7.2.2 Safety Assessments

The summaries and statistical analyses of the safety endpoints will be completed for the safety population. Safety endpoints include solicited adverse events, unsolicited adverse events, changes in laboratory values, and changes in vital signs. All solicited and unsolicited adverse events will be recorded by the Investigator in the AE eCRF, and all adverse event terms will be coded using MedDRA preferred term and system organ class.

7.2.2.1 Solicited Adverse Events

The severity rating (Grade 1, 2, or 3) assigned to each solicited adverse event will be summarized by the 7-day injection interval following each injection and by treatment group. The worst value (i.e., maximum severity) for each sign/symptom will also be summarized by injection interval and treatment group.

7.2.2.2 Unsolicited Adverse Events

All unsolicited adverse event terms will be coded using MedDRA. Summaries of the number (%) of subjects in each treatment group with at least one adverse event, classified according to MedDRA preferred term and system organ class, will be provided for:

- All adverse events
- Related adverse events
- Serious adverse events
- Potential immune-mediated medical conditions (PIMMCs)

Related adverse events are defined as adverse events that are possibly, probably, or definitely related to study injection, as assessed by the study Investigator. Fisher's exact tests will be used to compare the treatment groups with respect to the proportion of subjects with at least one adverse event.

The following additional summaries of unsolicited adverse events will also be provided:

- Incidence of adverse events after the first and second injections
- Incidence of adverse events by severity
- Incidence of adverse events by relationship to study injection

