3.2 Study Outcome Measures

3.2.1 Primary Outcome Measures

- The number of subjects experiencing solicited local injection site reactions within 7 days following each study injection.
- The number of subjects experiencing solicited systemic reactions within 7 days following each study injection.
- The number of subjects spontaneously reporting adverse events from Day 0 through Day 84.
- The number of serious adverse events considered related to any of the study injections reported at any point during the study period.

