For adverse events requiring immediate reporting, the PI and the Sponsor Medical Monitor both determine causality. It is expected that communication and consultation may occur in the assessment of the causality of adverse events. The greatest degree of causal relationship (definite > probable > possible > not related) determined by either the investigator or Medical Monitor after their discussions will determine the ultimate classification of the adverse event. Adverse events where the causality is not assessable will be considered related to the study injection.

Every effort should be made by the investigator to determine the existence of any pre-existing conditions that must be taken into consideration when assessing causal relationship of an adverse event. Pre-existing conditions should be recorded in the eCRF as baseline history and substantiated by appropriate source documentation. Intermittent conditions such as headaches in adults may not be present on Study Day 0 but may represent an adverse event if the frequency, intensity, or duration of the event is worse than usual following study injection.

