9.6.2 Rules for Suspension of the Entire Study

The study will be immediately suspended (paused) and no additional study injections administered, pending review and discussion of all appropriate safety data by the SMC, if one or more subjects in any treatment group experience any of the following adverse events:

- Anaphylaxis or bronchospasm within 4 hours of study injection indicative of an immediate hypersensitivity reaction to the vaccine and not attributable to another cause.
- Any systemic rash, including but not limited to urticaria, generalized petechiae, or erythema multiforme, not attributable to another cause.
- Tissue necrosis at the study injection site.
- Any other serious adverse event deemed to be possibly, probably, or definitely relatable to the study injection by the PI or Sponsor Medical Monitor, based on close temporal relationship or other factors.

The study will also be immediately suspended (paused) and no additional study injections administered pending review and discussion of all appropriate safety data by the SMC if three or more subjects experience the following AEs determined to be related to study injection:

- Changes in laboratory parameters that meet Grade 3 severity.
- High fever (oral temperature $\geq 102.2^{\circ}\text{F}/39^{\circ}\text{C}$) within 1 week following study injection associated with constitutional symptoms and not attributable to another cause.
- Severe injection site reactogenicity that involves Grade 3 local pain, induration, or erythema.

Study suspension or termination will only apply to additional study injections. Subjects for whom their study injections are discontinued will remain in limited visit follow-up for safety evaluations and immunology blood draws.

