11.5.2.2 Unsolicited Adverse Events

All unsolicited adverse event terms will be coded using MedDRA. Summaries of the number (%) of subjects in each treatment group with at least one adverse event, classified according to MedDRA preferred term and system organ class, will be provided for:

- All adverse events
- Related adverse events
- Serious adverse events
- PIMMCs

Related adverse events are defined as adverse events that are possibly, probably, or definitely related to study injection, as assessed by the study PI.

The following additional summaries of unsolicited adverse events will also be provided:

- Incidence of adverse events after the first and second injections
- Incidence of adverse events by severity of event

- Incidence of adverse events by relationship to study injection

The adverse event summaries described in the previous paragraphs will also be provided based on all (i.e., unsolicited and solicited) adverse events.

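### The analysis text defines related adverse events by the investigator alone, although protocol 9.2.3 sets the final causality of immediately reportable events as the higher of two assessors' grades

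*SAP*

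**What the plan says.** Protocol 9.2.3 sets out how causality is settled. The investigator grades every event on a four-level scale, from not related to definitely related. A further rule covers the most important events: "For adverse events requiring immediate reporting, the PI and the Sponsor Medical Monitor both determine causality". "The greatest degree of causal relationship (definite > probable > possible > not related) determined by either the investigator or Medical Monitor", once the two have conferred, "will determine the ultimate classification of the adverse event". The same paragraph adds: "Adverse events where the causality is not assessable will be considered related to the study injection". Protocol 9.4 makes SAEs immediately reportable, within 24 hours, so they fall under the two-assessor rule.

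Protocol 9.6.2 follows the same logic. One of its one-subject triggers for pausing the study is an SAE "deemed to be possibly, probably, or definitely relatable to the study injection by the PI or Sponsor Medical Monitor".

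The analysis text is different. Protocol 11.5.2.2 defines related events as those "possibly, probably, or definitely related to study injection, as assessed by the study PI". The SAP repeats this in 7.2.2.2: "Related adverse events are defined as adverse events that are possibly, probably, or definitely related to study injection, as assessed by the study Investigator". Neither section mentions the Medical Monitor's grade, the final classification or the rule for unassessable causality.

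Two other places use relatedness without naming an assessor. One is the fourth primary outcome in protocol 3.2.1: "The number of serious adverse events considered related to any of the study injections reported at any point during the study period". The other is the summary of related Grade 3 events in SAP 7.2.2.4.

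**The concern.** One event can carry two causality labels. It can be related when it is classified and when the pause rule is applied, and unrelated when it is tabulated. SAEs are the events for which relatedness matters most, and they are also the events to which the two-assessor rule applies.

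Related SAEs are a primary outcome, and few should be expected: protocol 2.3.1 reports no serious events in the three earlier ID93 + GLA-SE trials it summarises. With a count that is likely to be zero or close to it, the choice between two definitions of related can decide whether the report says none or one.

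Unassessable causality raises a similar question. The four-level scale in protocol 9.2.3 has no category for it, and protocol 11.5.2.5 rules out imputing missing values. An event left without a grade would not meet the definition in SAP 7.2.2.2, unless it had been coded as related before analysis.

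**Working it through.** The plan gives no figure on this point, so the check compares the rules and then adds an illustration of size.

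**1. The rules side by side**

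| Place | Who decides | Unassessable causality |
|---|---|---|
| Protocol 9.2.3 (immediately reportable events) | Higher of investigator and Sponsor Medical Monitor, after discussion | Related (stated for adverse events generally) |
| Protocol 9.6.2 (related-SAE pause trigger) | Investigator or Sponsor Medical Monitor | Not stated |
| Protocol 11.5.2.2 and SAP 7.2.2.2 (tables) | Investigator alone | Not stated |
| Protocol 3.2.1 (primary outcome) and SAP 7.2.2.4 (related Grade 3) | Not named | Not stated |

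**2. Where the two definitions disagree.** Two assessors with four grades each give 4 × 4 = 16 combinations. The tables count an event as related if the investigator's grade is possible or higher. Protocol 9.2.3 counts it as related if the higher of the two grades is possible or higher. These differ only when the investigator says not related and the Medical Monitor says possible, probable or definite: 3 of the 16 combinations. This counts the patterns that conflict. It does not estimate how often they occur.

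**3. Direction.** The higher of two grades is never below the investigator's own grade. Changing from the investigator-only rule to the 9.2.3 rule can therefore add related events but never remove one. Counting unassessable events as related works in the same direction.

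**4. Size, as an illustration.** Assume one such SAE in the single-vial arm and no other related SAE. SAP Table 1 lists 23 subjects in that arm and 25 in the two-vial arm. Exact (Clopper-Pearson) 95% limits are:
- 0/23: upper limit = 1 − 0.025^(1/23) = 14.8%.
- 1/23 = 4.3%: lower limit = 1 − 0.975^(1/23) = 0.1%. The upper limit solves (1 − p)^23 + 23p(1 − p)^22 = 0.025, giving 21.9%.
- If the event were in the two-vial arm instead: 0/25 has an upper limit of 13.7%, and 1/25 = 4.0% has limits of 0.1% to 20.4%.

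The primary outcome is a number of events, so its own change is from 0 to 1. The proportions show what that means per arm when the event belongs to one subject.

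**5. Where the event would still be visible.** SAP 7.2.2.2 summarises all adverse events and all SAEs whatever their causality. Table 14.2.6 covers SAEs, Listing 16.10 covers deaths, SAEs and PIMMCs, and Listing 16.11 covers subjects who meet a criterion for suspending injection. The event would be missing from the related-AE tables (14.2.3 and 14.2.4). It would also be missing from the primary related-SAE count if the same definition is applied there.

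**The case against.** The best case against acting is that the gap is narrow and the event is not hidden. Much of that stands.

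- A reader might infer that the SAP departed from the protocol. It did not. Protocol 11.5.2.2 already uses the investigator alone, and the SAP follows it. The conflict is between two sections of the protocol.
- A reader might infer that an SAE that stopped dosing could disappear from the report. The SAE table and Listings 16.10 and 16.11 rule that out. Under protocol 9.7.2 the SMC also meets if halting criteria are met and reviews cumulative unblinded safety data at the end.
- A reader might infer that the primary outcome is undercounted. The documents do not settle this. Protocol 3.2.1 names no assessor, and nothing says that the definition in SAP 7.2.2.2 overrides the final classification for that outcome.
- A reader might infer that one reclassified event would decide the trial. Protocol 11.3 says that the study tests no formal hypothesis. One event against none, 1/23 versus 0/25, gives a two-sided Fisher p of 23/48 = 0.48, and the intervals for 0/23 and 1/23 overlap heavily.
- The two-assessor gap needs an immediately reportable event, disagreement that survives discussion, and an investigator grade of not related. On the pausing side it concerns only the related-SAE trigger. The anaphylaxis or bronchospasm, systemic rash and necrosis triggers do not use that grade, and the three-subject rule does not say who determines relatedness.
- The rule for unassessable causality may be applied before the data reach analysis, in which case nothing is lost. The documents do not say whether it is.

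These points limit how often the problem can arise and what follows from it. They do not remove the contradiction. Neither analysis section says that the final classification is the variable tabulated, and SAP 7.2.2.2 is the only definition of related in the SAP.

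**Conclusion.** The inconsistency is real, and its effect runs in one direction. Applied literally, the investigator-only definition can leave out of the related-AE tables an SAE that protocol 9.2.3 classifies as related and that meets the related-SAE pause trigger in 9.6.2. Its absence from the primary related-SAE count depends on the same definition being used there. Omission of an unassessable event depends on its not having been coded as related beforehand.

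The likely size is zero or very few events. The change from 0/23 to 1/23 rests on an assumed event, since the documents do not show that one occurred. The point merits correction because the count is small, the outcome is primary and the remedy is cheap. It is not evidence that the completed safety tables are wrong.

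**What to change.** Reconcile protocol 9.2.3, protocol 11.5.2.2 and SAP 7.2.2.2 with one analysis definition. An event is related if its final classification under protocol 9.2.3 is possible, probable or definite. For immediately reportable events this is the higher of the two grades after discussion. For all other events it is the investigator's grade. Events of unassessable causality count as related.

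Apply the definition to Tables 14.2.3 and 14.2.4, to the related Grade 3 summary in SAP 7.2.2.4, and to the primary count of related SAEs. Table 14.2.6 needs no change on this account, because its title does not split SAEs by relatedness. Show both assessors' grades in Listing 16.10.

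The SAP introduction says that the safety analysis has already been performed and that the amendment touches only the immunology section, so new wording alone is not enough. The study report should say which causality variable was used. The sponsor should check the few immediately reportable or unassessable events and rerun the tables only if a classification differs. If none does, one sentence saying so closes the matter.

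The cost is a sentence of definition and a small re-check. The related count may become slightly less favourable. No new data or statistical method is needed, and the pause rule is left as it stands.

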7.2.2.3 Reactogenicity Adverse Events

Local injection site reaction adverse events (pain, induration, and erythema) and solicited systemic reaction adverse events (headache, arthralgia, chills, loss of appetite, fever, fatigue, and myalgia) will be recorded at 60 minutes and seven days after each study injection (Days 0, 7, 56, and 63). The seven day period following each study injection is referred to as the 'post-injection period'. Study injection reactions will be classified as occurring during the corresponding 7-day post-injection period (Post Injection Period Day 0-7, and 56-63) if the onset date is on or after the date and time of injection and before the seventh day after injection.

Summaries of the number (%) of subjects in each treatment group with at least one reactogenicity adverse event reported in the CRF will be provided for:

- at least one local injection site reaction
- at least one systemic reaction
- each individual event

The distribution of the maximum severity grade for the 7-day post-injection period will be summarized for each adverse event. If a subject experienced an adverse event more than once, the event with the maximum severity grade will be included in this summary.

Primary analysis of reactogenicity adverse events will be conducted in an Intent to Treat manner, that is, subjects will be classified based on the treatment group to which they were assigned. If any subjects incorrectly received an injection of product they were not assigned to receive, secondary analysis will be conducted with subjects classified based on product actually received during the study. Any subject randomized (ITT) but not enrolled (did not receive a study injection) will not be included in any analyses.

Fisher's exact tests will be used to compare the treatment groups with respect to the proportion of subjects with at least one reactogenicity adverse event. Fisher's exact tests will also be used to compare the treatment groups with respect to local site of injection reactions and solicited systemic reactions separately.

Reactogenicity adverse events will be summarized by treatment group for each 7-day post-injection period. The treatment groups will be compared with respect to the number (%) of subjects with at least one reactogenicity adverse event during each 7-day post-injection period using Fisher's exact tests.

The following proportions of adverse events will be compared across treatment groups:

- Proportion of subjects with at least one local site of injection reaction
- Proportion of subjects with at least one systemic reaction adverse event
- Proportion of subjects with at least one local site of injection reaction in each post-injection period (Post Injection Periods Day 0-7 and 56-63)
- Proportion of subjects with at least one systemic reaction adverse event in each post-injection period (Post Injection Periods Day 0-7 and 56-63)

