2.3 Potential Risks and Benefits

2.3.1 Potential Risks

Safety data from the TBVPX-113, -114, and -203 trials of ID93 + GLA-SE are summarized here.

The vaccine (combined ID93 + GLA-SE) was safe and well-tolerated:

- The most common adverse events were injection site reactions (pain/tenderness, erythema, and induration) and certain injection-associated systemic reactions (headache, fatigue, myalgia, anorexia, chills, and arthralgia). The majority of adverse events were graded as mild (Grade 1).
- There were no clinically significant changes in clinical chemistry or hematology values though there were subjects that experienced Grade 1 and Grade 2 fluctuations in clinical chemistry and hematology values (including decreased hemoglobin, neutrophils, lymphocytes, and WBC).

These findings were typically mild and transient, typical of vaccinations by the IM route, and indicative of the expected immunomodulatory effect of GLA-SE. There were no Grade 4 AEs, nor were there any serious AEs, AEs defined as a dose-limiting toxicity, or AEs of special interest (AEs of special interest were renamed Potential Immune-Mediated Medical Conditions (PIMMCs)). No subjects withdrew from the studies because of an AE.

GLA-SE has been tested in numerous clinical trials in combination with a wide variety of antigens for infectious diseases including influenza, leishmaniasis, leprosy, schistosomiasis, and malaria. Several trials evaluated GLA-SE given alone or in combination with an antigen as a cancer immunotherapy.

These clinical trials are evaluating GLA-SE at dose levels ranging from 0.5 to 20 µg. In these studies, over 1100 subjects have received at least one study injection containing GLA-SE. Safety data have not revealed any significant safety issues at any dose level tested. These studies have revealed an acceptable safety profile:

- Study injections are generally well tolerated
- There have been no serious adverse events related to study injection
- Injection site reactions are common and may include pain, tenderness, erythema, and induration
- Systemic reactions may include headache, fatigue, anorexia, fever, chills, myalgia, arthralgia, and anorexia
- Transient elevations in CRP levels were noted in one study
- Hematologic changes may occur (including decreases in hemoglobin, WBC, lymphocytes, and neutrophils).

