2.1 Primary Objectives

- To evaluate the safety and tolerability of single-vial lyophilized ID93 + GLA-SE following two intramuscular (IM) injections administered on Days 0 and 56.
- To compare the safety and tolerability of single-vial lyophilized ID93 + GLA-SE to the two-vial presentation consisting of lyophilized ID93 and liquid GLA-SE following two IM injections administered on Days 0 and 56.

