7.2 Plan for Statistical Summaries and Analyses

7.2.1 General Considerations

Statistical summaries and analyses of baseline and safety data will be provided for the safety population, defined as all subjects who receive at least one study injection. Summaries and analyses of immune response data will be provided for the per-protocol population. The objectives of the immune response statistical summaries and analyses are to assess the immunogenicity following intramuscular administration of study vaccine among the treatment groups. The goals are:

1. To describe the humoral and cellular response to both vaccine presentations in terms of magnitude and positive response rate
2. To determine if there is a significant difference in the immune response elicited by the two-vial and the single-vial lyophilized vaccine presentation

All individual subject data listings will be provided in appendices to the clinical study report. Data will be summarized and tabulated by treatment group and descriptive statistics will be provided where

appropriate. The immunology analysis will be performed using either SAS version 9.3 or higher or R version 3.5 or higher.

Categorical data will be analyzed using Fisher's exact test using 0.05 level of significance ($\alpha = 0.05$) with Holm-Bonferroni adjustments whenever pairwise comparisons are made between more than two categories.

Continuous data will be compared between two treatment groups using a Two-sample T-test if the normality assumption is met or Wilcoxon Rank-Sum Test, otherwise. Response rates will be compared using a Fisher's Exact test. Significant differences will be detected based on a two-sided test with $p \leq 0.05$ ($\alpha = 0.05$). Comparisons will be accompanied by the point-estimate and 95% CI for each group.

Missing data: The analysis plan assumes that missing data are missing completely at random (MCAR) and analysis will be performed on the available data.

Individual subject data listings will be provided as separate appendices in the CSR. All summaries, statistical analyses, and individual subject data listings will be analyzed by using either SAS version 9.3 or higher or R version 3.5 or higher.

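### Severity of solicited reactions is tabulated by arm, but no between-arm test or effect estimate in SAP 7.2.2.3 uses it

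*SAP*

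**What the plan says.** One of the two primary objectives is comparative: "To compare the safety and tolerability of single-vial lyophilized ID93 + GLA-SE to the two-vial presentation" (SAP 2.1). For reactogenicity, SAP 7.2.2.3 says that Fisher's "exact tests will be used to compare the treatment groups with respect to the proportion of subjects with at least one reactogenicity adverse event". It applies the same test to local and to systemic reactions separately and to each 7-day period. The closing list of comparisons includes "Proportion of subjects with at least one local site of injection reaction in each post-injection period" and its systemic counterpart, with no grade threshold. This follows the protocol's primary outcome, "The number of subjects experiencing solicited local injection site reactions within 7 days following each study injection" (Protocol 3.2.1).

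Severity is handled descriptively. "The distribution of the maximum severity grade for the 7-day post-injection period will be summarized for each adverse event" (SAP 7.2.2.3). SAP 7.2.2.1 summarises maximum severity for each sign or symptom by injection interval and treatment group. Tables 14.2.7 and 14.2.8 show local and systemic reactions by period and severity. SAP 7.2.2.4 counts subjects with related Grade 3 events by arm and adds narratives. None of these places names a test, a difference or a ratio between arms.

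On expected frequency, Protocol 2.3.1 gives no percentage: "Injection site reactions are common and may include pain, tenderness, erythema, and induration", and most adverse events in earlier trials were Grade 1.

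**The concern.** Protocol 9.1 assesses safety by both the frequency and the severity of events, solicited reactions included. Protocol 2.3.1 says that the adjuvant often raises both the rate and the severity of reactogenicity compared with antigen alone. Grade also has consequences in the trial: Grade 3 local reactions appear in the individual and study-level halting rules (Protocol 9.6). Yet the formal comparison separates only reactors from non-reactors. A mild and a severe reaction count the same.

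This is the first trial of the single-vial product, and Protocol 2.2 calls it a bridging study. If the new presentation moved subjects from mild to moderate or severe reactions, the any-grade proportions could be nearly equal and every planned p-value unremarkable. A non-significant result could then be taken as evidence of similar tolerability, with no interval to show how much worsening in grade the data leave open.

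**Working it through.** **The plan's own figure.** No power is stated for the between-arm comparison. The only operating characteristic is Protocol Table 2, the chance of seeing at least one event, 1 − (1 − p)^n. For p = 0.05 it gives 40%, 64% and 79% at n = 10, 20 and 30, as printed, and all 12 cells reproduce. At 23 to 25 per arm the same formula gives 69% to 72%. The table does not address a comparison of arms.

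**Inputs.** Group sizes are 25 two-vial and 23 single-vial (SAP Table 1; 24 and 24 were planned). SAP 7.2.1 sets Fisher's "exact test using 0.05 level of significance". It also says "Significant differences will be detected based on a two-sided test", in its paragraph on continuous data and response rates; I assume that this covers the safety tests. No dropout is assumed. All reaction rates and grade mixes below are assumptions, because the documents give none.

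**Near the ceiling.** Suppose all 23 single-vial subjects react.
- With 20 of 25 two-vial reactors, all five non-reactors are in one arm: p = [C(25,5) + C(23,5)] / C(48,5) = (53,130 + 33,649) / 1,712,304 = 0.051.
- With 19 of 25, p = [C(25,6) + C(23,6)] / C(48,6) = (177,100 + 100,947) / 12,271,512 = 0.023.

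So even with every single-vial subject reacting, significance needs a two-vial rate of 19/25 = 76% or less.

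**Fisher power on any grade.** Power is the sum, over all pairs of counts with p ≤ 0.05, of the product of the two binomial probabilities.

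| Two-vial rate | Same rate (size) | Single-vial 95% | Single-vial 100% |
|---|---|---|---|
| 50% | 4.0% | 96% | 99.8% |
| 70% | 3.4% | 57% | 81% |
| 80% | 3.5% | 21% | 38% |
| 85% | 3.3% | 7.8% | 16% |
| 90% | 2.4% | 1.6% | 3.3% |
| 95% | 0.8% | 0.8% | 0.1% |

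The size column is also the rejection rate when only severity worsens: about 1% to 4%.

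**General shift to higher grades.** Each cumulative odds of reaching grade 1, 2 or 3 is multiplied by a common odds ratio (OR). From a none/mild/moderate/severe mix of 10/60/25/5% with OR 3:
- any grade: odds 0.90/0.10 = 9, times 3 = 27, so 27/28 = 96.4%
- Grade 2 or 3: odds 0.30/0.70 = 0.429, times 3 = 1.286, so 56%
- Grade 3: odds 0.05/0.95 = 0.0526, times 3 = 0.158, so 13.6%

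The any-grade rate moves by about 6 percentage points and the Grade 2 or 3 rate by about 26. Below, Fisher on any grade is exact; the tie-corrected Wilcoxon rank-sum test on grade 0–3 is simulated.

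| Two-vial mix (%) | OR 3: Fisher v rank | OR 5: Fisher v rank |
|---|---|---|
| 10/60/25/5 | 2% v 50% | 2% v 82% |
| 20/55/20/5 | 14% v 50% | 22% v 82% |
| 30/50/15/5 | 25% v 51% | 43% v 83% |
| 50/37/11/2 | 41% v 52% | 66% v 83% |

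With no difference between arms, the rank test rejected in 4.5% to 5.4% of simulations.

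**Severity worsens, same number of reactors.**

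| Two-vial to single-vial mix (%) | Fisher | Rank |
|---|---|---|
| 10/70/18/2 to 10/45/36/9 | 2.4% | 35% |
| 10/70/18/2 to 10/31.5/40.5/18 | 2.4% | 69% |
| 20/60/18/2 to 20/28/36/16 | 3.5% | 43% |
| 50/35/13/2 to 50/17.5/22.5/10 | 4.0% | 10% |

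The rank test's advantage shrinks as non-reactors become more numerous.

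**Where Fisher does better.** If the change is mainly from none to mild, say 50/37/11/2 to 15/72/11/2, Fisher has 71% power and the rank test about 54%.

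**The case against.** The any-grade count is the protocol's own primary outcome, and Fisher's test analyses exactly that. The documents say that 48 subjects was not a power-based number (Protocol 11.1, SAP 7.1) and that no formal hypothesis is tested (Protocol 11.3). Low power is therefore disclosed and is not in itself an error. All of this stands. It explains the sample size, but not why the between-arm tests, once planned, leave out grade.

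A reader might infer that the plan throws severity away. It does not: grade is shown by arm and period, and related Grade 3 events are counted by arm. A marked shift would be visible in the tables. What is missing is a between-arm estimate or test. The general statement in SAP 7.2.1 that categorical data are analysed with Fisher's test could be stretched to cover the severity tables, but no such comparison is named.

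A reader might also infer that the primary comparison has almost no ability to find a worse profile. That needs a rate near the ceiling, and the documents say only that reactions are common. Appendix 4 grades erythema and induration under 2.5 cm as 0, which lowers the any-grade rate for those signs. No rate is given for systemic reactions, on which half of the listed comparisons rest. At lower rates Fisher has useful power.

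Finally, a proportional-odds shift suits a rank test, so those simulations favour it. The none-to-mild case shows that it is not uniformly better.

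**Conclusion.** The point holds in a limited form. Severity is described by arm but not compared. The planned tests cannot pick up a change in severity alone: they reject at about 1% to 4% for any-grade rates of 50% to 95%. For a general shift to higher grades they are weak if the two-vial rate is about 85% or more (power 16% or less even if every single-vial subject reacts), and the gap to a rank test narrows at lower rates. These figures rest on 25 and 23 subjects, a two-sided 0.05 level, no dropout and assumed grade mixes.

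An added grade-based test would not make the trial decisive. Its power is about 50% at OR 3, and it is low for a severity-only change when half the subjects do not react. Its main value is an odds ratio with an interval. Nor do the documents support replacing the any-grade tests or making them secondary: they match the stated outcome, and the SAP introduction says that the safety analysis has already been performed. This is a cheap improvement, not the repair of an invalid analysis.

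**What to change.** Keep the pre-specified any-grade Fisher tests as they are. Add a supplementary analysis, clearly labelled post hoc:

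- Derive each subject's maximum grade (0, 1, 2, 3) across the local signs and, separately, across the systemic signs, for each post-injection period and overall. The SAP takes the maximum per sign or event, so this is a new variable.
- Compare the arms with a Wilcoxon rank-sum or exact trend test.
- Report a common odds ratio with its 95% CI. SAP 7.2.1 promises intervals only for each group, so this supplies the missing between-arm estimate.

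The cost is SAP wording, the derived variable and additions to the reactogenicity tables, with no new data. The downsides are about six more p-values (two reaction classes × [two periods + overall] = 6), sparse Grade 3 cells that may make the odds ratio unstable, and post hoc status, which limits the result to supporting interpretation.
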